#### 2.3.1.3 Worsening of Symptoms/Delay in Treatment

There could be a delay in treatment for as long as 16 weeks from the initial screening visit; this period of time includes the taper off medications, the drug free period, and the double-blind study phase. There may be a worsening of depressive and anxiety symptoms, including suicidal ideation, as the patient's psychotropic medications are discontinued. Subjects will be told to immediately inform their research physician if they develop suicidal ideation or symptoms of mania, or a worsening of depressive symptoms. We have included safety measures such as discontinuation of the study drug and transition to standard clinical treatment should subjects worsen to a sufficient degree. These precautions are likely to be effective in minimizing risks.

#### **2.3.1.4 Blood Draw**

Venipuncture or intravenous lines may be associated with the momentary discomfort of the needle stick, as well as a small potential risk of hematoma (bruise) formation.

The total amount of research blood drawn during the whole study will not be more than 370mL during the 14-16 week study.

### 2.3.1.5 Clinical Rating Scales

The risks and discomforts of clinical ratings or psychological assessments are minimal. No discomfort is expected to occur during clinical interviews or psychological assessments, other than the potential emotional stress caused by discussing difficult psychiatric topics.

# 2.3.1.6 Neurocognitive Battery

There are also minimal risks associated with the neurocognitive tasks, beyond possible stress or frustration. Participants will be informed that they can stop participation in these tasks at any time.

#### 2.3.1.7 MEG

MEG is associated with minimal medical risk or discomfort. Remaining still for the duration of the scan may result in mild muscle stiffness or fatigue.

The potential risks associated with MEG will be minimized as follows:

• In addition to a Basic Life Support (BLS)-certified staff member, ancillary staff will be present throughout in case of emergency.

#### 2.3.1.8 MRI

There is minimal risk associated with exposure to magnetic waves during MR imaging, though the potential risk of heart rhythm disturbances exists for patients with a history of heart rhythm abnormalities or those who have certain types of pacemakers. A substantial risk to persons who have metallic objects inside their bodies exists, as the magnet in the scanner can cause these to move. Pregnant women should not undergo MRI because of the possible harmful effects to the fetus. People with claustrophobia may find this procedure uncomfortable as it involves having one's head confined to a relatively small space. A small amount of discomfort may be associated with having to be still for the 90 minutes required for the MR scan, possibly resulting in mild muscle stiffness and fatigue. In addition, very high field magnets (above 3 Tesla) may cause additional side-effects of peripheral nerve stimulation. This is experienced as twitching in the muscles, or a tingling sensation. Additionally, some subjects report dizziness, mild nausea, headache, a metallic taste in their mouth, or a sensation of flashing lights. These sensations are not considered harmful and desist upon cessation of scanning. On very rare occasions, subjects may experience some eye discomfort. No biological hazards to humans have been associated with high static magnetic fields. Finally, the MRI scanning procedure is loud, and may affect hearing; we will place earplugs to wear during the scan to minimize discomfort and prevent adverse effects on hearing.

The potential risks associated with MRI will be minimized as follows:

- The potential for claustrophobia will be mitigated by explaining the nature of the procedure in detail prior to entering the MR scanner.
- In addition to a BLS-certified staff member, ancillary staff will be present throughout in case of emergency.
- A member of the research team will place hearing protection, such as earplugs, in each subject to be worn during the scan to minimize discomfort and prevent any adverse effects on hearing.
- A history of any intraocular, intra-aural, intracranial, or intra-thoracic ferromagnetic implants or devices is an exclusion criterion. Ferromagnetic objects can be heated and/or moved in a strong magnetic field (3T and 7T), which may result in bodily harm.
- Women of child-bearing potential will undergo urine pregnancy testing to rule out pregnancy no more than 24 hours prior to each imaging session.
- A power meter will be used to ensure that experimental sequences fall within the
  accepted guidelines for radio frequency (RF) energy exposure. Applied RF power
  will be limited so that the specific absorption averaged over the head does not exceed
  3W/kg for 10 minutes.
- While subjects are in the scanner, it is standard procedure to provide them with a
  squeeze bulb. Subjects are instructed to squeeze it in case of emergency (e.g. eye
  discomfort, nausea, emesis), after which the scan will stop immediately. If subjects
  experience eye discomfort or desire to stop for any reason, the scan will stop
  immediately.

#### 2.3.1.9 Standard Treatment Phase

During the optional traditional standard treatment phase, participants may have worsening of symptoms, including suicidal ideation, as medications and dosages are adjusted. In addition, pharmacologic treatment may result in side effects.

At the end of study participation, patients with MDD will be offered short-term traditional standard treatment (up to two months). During this period, patients will be assessed and discussed at daily morning rounds by nursing staff and licensed independent practitioners (MD, APRN, part of the research team) for changes in psychiatric symptomatology and medication side effects. Additional interventions will be made depending on their status/progress. Additionally, our branch holds several weekly meetings to discuss our inpatients in the standard treatment phase, including an interdisciplinary treatment team meeting. During this meeting, ancillary team members not typically present at morning rounds (e.g., physical therapy, occupational therapy, pharmacy) will also have the opportunity to present their observations and weigh in on patient progress. If issues arise - for instance, psychiatric decompensation or intolerable side effects- medications may be adjusted/discontinued and/or additional medications or therapeutic interventions initiated based on a risk-benefit discussion between the inpatient treatment team and the patient. Additionally, if the patient expresses suicidal or homicidal thinking in the treatment phase, is judged to be an imminent risk of harm to self and/or others, and is not amenable to additional voluntary treatment on 7SE, he or she may be involuntarily psychiatrically hospitalized for his or her safety at an outside hospital.

#### 2.3.2 Known Potential Benefits

This study offers no direct benefits to participants but is likely to yield important and generalizable knowledge about the development of new treatments for MDD.

## 2.3.3 Assessment of Potential Risks and Benefits

The primary risks of study participation include possible adverse events associated with TS-161, discomfort during the medication taper and drug-free periods, and mild discomfort resulting from blood draws, imaging procedures. This study is likely to yield generalizable knowledge about the antidepressant effects of TS-161. Overall, the risks are reasonable in relation to anticipated benefit.

## 3 OBJECTIVES AND ENDPOINTS

OBJECTIVES	ENDPOINTS	JUSTIFICATION FOR ENDPOINTS
Primary		
To evaluate the ability of the mGlu2/3 receptor antagonist prodrug, TS-161, to improve overall depressive	Montgomery-Asberg Depression Rating Scale (MADRS) change from baseline	The MADRS is a tool used for the evaluation of depressive symptoms in adults and for the assessment

OBJECTIVES	ENDPOINTS	JUSTIFICATION FOR ENDPOINTS
symptomatology in subjects with MDD. The efficacy of a three-week course of TS-161 will be compared to three weeks of placebo in a crossover study. The Montgomery-Asberg Depression Rating Scale (MADRS) will serve as the main outcome measure.		of any changes to those symptoms.
Hypothesis: Among TRD-MDD subjects, the active drug (TS-161; 50-100 mg/day) will result in less severe depressive symptoms than placebo after three weeks of treatment.		
Secondary		
1. To evaluate the antidepressant efficacy of TS-161 230 min and 1, 2, 3, 7, and 14 days postinitial dosing compared to placebo in a crossover study.	Change from baseline on MADRS total scores	1. The MADRS is a tool used for the evaluation of depressive symptoms in adults and for the assessment of any changes to those symptoms.
Hypothesis: Among TRD-MDD subjects, the active drug (TS-161; 50-100 mg/day) compared to placebo will result in less severe depressive symptoms than placebo 230 min, 1, 2, 3, 7, and 14 days post-initial dosing.		
2. To determine whether TS- 161 will demonstrate a superior antidepressant efficacy compared to	2. Proportion of subjects in remission (defined as MADRS total score ≤10)	2. The MADRS is a tool used for the evaluation of depressive symptoms in adults and for the

OBJECTIVES	ENDPOINTS	JUSTIFICATION FOR ENDPOINTS
placebo in a crossover study		assessment of any changes to those symptoms.
Hypothesis:		
Among TRD-MDD subjects, the active drug compared to placebo will result in a greater proportion of subjects in remission at 230 min, 1, 2, 3, 7, and 14 days post-initial dosing.		
3. To determine whether TS-161 will demonstrate a superior antidepressant response compared to placebo in a crossover study.	3. Proportion of subjects achieving response (defined as a ≥50% reduction from baseline in MADRS total score).	3. The MADRS is a tool used for the evaluation of depressive symptoms in adults and for the assessment of any changes to those symptoms.
Hypothesis:		
Among TRD-MDD subjects, the active drug compared to placebo will result in a greater proportion of responders at 230 min, 1, 2, 3, 7, 14, and 21 days post-initial dosing.		
4. To evaluate the antisuicidal ideation effects of TS-161 at 230 min, 1, 2, 3, 7, 14, and 21 days post-initial dosing compared to placebo in a cross over study.	4. Change from baseline on item 10 (suicidality) of the MADRS and total score on the C-SSRS, and the Scale for Suicidal Ideation (SSI).	4. Item-10 of the MADRS used to assess suicidal ideation.
Hypothesis:		
Among TRD-MDD subjects, the active drug will result in less severe suicidal ideation than placebo at 230 min, 1, 2, 3, 7, 14, and 21 days postinitial dosing.		
5. To investigate the effects of TS-161 on mood,	5. Change from baseline on the HDRS, HAM-A, the	5. These rating scales evaluate various aspects of

OBJECTIVES	ENDPOINTS	JUSTIFICATION FOR ENDPOINTS
anxiety, and anhedonia symptoms at 230 min, 1, 2, 3, 7, 14, and 21 days postinitial dosing compared to placebo in a cross over study.	PANAS, Snaith–Hamilton Pleasure Scale (SHAPS), and the Temporal Experience of Pleasure Scale (TEPS) scales.	mood, anxiety, and anhedonia.
Hypothesis: Among TRD-MDD subjects, TS-161 will result in less severe mood, anxiety, and anhedonia symptoms than placebo at 230 min, 1, 2, 3, 7, 14, and 21 days post-initial dosing.		
6. To assess the safety and tolerability of a three-week course of TS-161 compared to placebo in a crossover study.  Hypothesis: Among TRD-MDD subjects, the active drug will result in comparable safety and tolerability to placebo at the different timepoints measured during the 3 weeks of treatment.	6. Incidence of AEs and total scores using the Clinician Administered Dissociative States Scale (CADSS), Young Mania Rating Scale (YMRS), the Brief Psychiatric Rating Scale (BPRS), vital signs, changes in clinical laboratory evaluations, and ECGs.	6. These measures and evaluations assess various aspects of clinical condition, adverse events, and mood and anxiety symptomology.

OBJECTIVES	ENDPOINTS	JUSTIFICATION FOR ENDPOINTS
Surrogate Markers of Drug Effect, Target Engagement, and Antidepressant Response  1. To determine whether the glutamate peak in the medial PFC (mPFC) correlates with changes in depression scores to TS-161.  Hypothesis 1:  Among TRD-MDD subjects, pre-treatment mPFC glutamate levels will predict the magnitude of clinical improvement to TS-161 in subjects with MDD, but not to placebo.  Hypothesis 2:  Among TRD-MDD subjects, post-treatment increases in glutamate levels will predict the magnitude of clinical improvement to TS-161 (but not placebo).	1.  H-MRS correlates with changes in MADRS score	1. The MADRS is a tool used for the evaluation of depressive symptoms in adults and for the assessment of any changes to those symptoms. MRS is used to measure glutamate levels.
2. To determine whether gamma power increases with TS-161are associated with treatment response to TS-161.	Gamma power measured via MEG	MEG scanning is used to measure gamma power.
Hypothesis 1: Among TRD-MDD subjects, pre-treatment gamma power levels will predict the magnitude of clinical improvement to TS-161, but not to placebo.		

OBJECTIVES	ENDPOINTS	JUSTIFICATION FOR ENDPOINTS
Hypothesis 2: Among TRD-MDD subjects, post-treatment increases in gamma power will be positively associated with antidepressant response to TS-161 (but not placebo).		
3. To determine whether TS-161 modulates task-dependent and resting-state activity in the frontolimbic circuitry and whether changes in activity in the frontolimbic circuitry are correlated with antidepressant response to TS-161	3. Changes in activity in the frontolimbic circuitry	3. fMRI is used to measure frontolimbic circuitry
Hypothesis 1:  Among TRD-MDD subjects, TS-161 administration will increase pgACC activity and decrease amygdala activity to emotional faces more than placebo. Similar effects will be observed in activity associated with the restingstate networks. TS-161 will also decrease pgACC activity during the tasks more than placebo.		
Tertiary/Exploratory		
1. To determine whether TS- 161 will increase plasma/serum BDNF and vascular endothelial growth factor (VEGF) and decrease glycine/serine and alter oxidative stress/inflammatory parameters in peripheral	1. Plasma/serum BDNF, vascular endothelial growth factor (VEGF), glycine/serine, and oxidative stress/inflammatory parameters in peripheral leukocytes	1. To identify potential biomarkers of TS-161 antidepressant activity.

OBJECTIVES	ENDPOINTS	JUSTIFICATION FOR ENDPOINTS
leukocytes compared to placebo and/or baseline levels.		
1. To collect blood samples for optional exploratory studies focusing on identification of genes, proteins, and metabolic responses that may influence the disposition, efficacy, safety and tolerability of TS-161.	2. Blood samples for the identification of genes, proteins, and metabolic responses	2. To identify potential biomarkers of TS-161 antidepressant activity.
3. To evaluate neurocognitive functioning on TS-161 compared to placebo and/or baseline levels.	3. Neurocognitive functioning	3. To evaluate any neurocognitive effects of TS-161

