Day 7	Clinical Rating Scales ii AE Assessments Sample Collection: Research Blood, PK Blood, Safety Labs iii, エラー! ブックマークが定義されていません。 Study Drug Administration: TS-161/ Placebo (100mg or 50mg) v Clinical Evaluations: Orthostatic Vital Signs, Physical Exam
Day 8	Study Drug Administration: TS-161/ Placebo (100mg or 50mg) V Clinical Evaluations: Orthostatic Vital Signs
Day 9	Study Drug Administration: TS-161/ Placebo (100mg or 50mg) V Clinical Evaluations: Orthostatic Vital Signs
Day 10	Study Drug Administration: TS-161/ Placebo (100mg or 50mg) v Clinical Evaluations: Orthostatic Vital Signs
Day 11	Study Drug Administration: TS-161/ Placebo (100mg or 50mg) v Clinical Evaluations: Orthostatic Vital Signs
Day 12	Study Drug Administration: TS-161/ Placebo (100mg or 50mg) v Clinical Evaluations: Orthostatic Vital Signs
Day 13	Study Drug Administration: TS-161/ Placebo (100mg or 50mg) v

Timepoint i	Procedures
	Clinical Evaluations: Orthostatic Vital Signs
Day 14	Clinical Rating Scales ii AE Assessments Sample Collection: Research Blood, PK Blood, Safety Labs エラー! ブックマークが定義されていません。,エラー! ブックマークが定義されていません。 Study Drug Administration: TS-161/ Placebo (100mg or 50mg)v
	Clinical Evaluations: Orthostatic Vital Signs
Day 15	Study Drug Administration: TS-161/ Placebo (100mg or 50mg) Clinical Evaluations: Orthostatic Vital Signs
Day 16	Study Drug Administration: TS-161/ Placebo (100mg or 50mg) Clinical Evaluations: Orthostatic Vital Signs
Day 17	Study Drug Administration: TS-161/ Placebo (100mg or 50mg) Clinical Evaluations: Orthostatic Vital Signs
Day 18	Study Drug Administration: TS-161/ Placebo (100mg or 50mg) Clinical Evaluations: Orthostatic Vital Signs
Day 19	Study Drug Administration: TS-161/ Placebo (100mg or 50mg) Sample Collection: Urine pregnancy test Clinical Evaluations: Orthostatic Vital Signs
Day 20	Sample Collection: Research Blood, PK Blood, Safety Labs iii Neurocognitive Battery Imaging: fMRI/MRS, MEG Study Drug Administration: TS-161/ Placebo (100mg or 50mg) Clinical Evaluations: Orthostatic Vital Signs, Weight & Height, ECG
Day 21 to Day 34	Washout Period
Day 21	Clinical Rating Scales ii AE Assessments

Timepoint i	Procedures
Day 28 to Day 33	Neurocognitive Battery  Imaging: Clinical MRI, fMRI/MRS, MEG

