We will also evaluate the putative neurobiological mechanisms involved in the antidepressant response to TS-161. We expect that this effect may modulate glutamate transmission and reverse the clinical symptoms of depression. The demonstration that an mGlu2/3 receptor antagonist produces antidepressant effects without psychotomimetic side effects would support the therapeutic relevance of the mGlu2/3 receptor and could direct the development of novel drug targets for the treatment of depression.

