# Brief Psychiatric Rating Scale (BPRS, (Overall and Gorham 1962))

Symptoms and behaviors that are characteristic of schizophrenia will be assessed by using the BPRS. Four key BPRS items will be used as an index of positive symptoms of schizophrenia based on previous reports that indicated their utility and validity (Bowers, Heninger et al. 1980, Kane, Honigfeld et al. 1988) and inclusion within the empirically derived thought disorder factor of the BPRS. These four key positive symptoms are conceptual disorganization, hallucinatory behavior, suspiciousness, and unusual thought content. Three key BPRS items, blunted affect, emotional withdrawal, and motor retardation are selected as a measure of negative symptoms of schizophrenia based on a report of their reliability and validity and their inclusion within the empirically derived withdrawal-retardation factor of the BPRS.

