## 9.1.2 Secondary Endpoints

- Proportion of subjects in remission (defined as MADRS total score  $\leq 10$ ).
  - H0: The 95% confidence interval for the odds ratio (TS-161 versus placebo) predicting MADRS total score ≤10 at 3 weeks will include one.
  - HA: The 95% confidence interval for the odds ratio (TS-161 versus placebo) predicting MADRS total score ≤10 at 3 weeks will be greater than and exclude one.
- Proportion of subjects with response (defined as ≥50% reduction from baseline in MADRS total score).
  - H0: The 95% confidence interval for the odds ratio (TS-161 versus placebo) predicting 50% change from baseline in MADRS total score at 3 weeks will include one.
  - HA: The 95% confidence interval for the odds ratio (TS-161 versus placebo) predicting 50% change from baseline in MADRS total score at 3 weeks will be greater than and exclude one.
- Change from baseline in HDRS, BPRS, CADSS, C-SSRS, HAM-A, MADRS, PANAS, SHAPS, SSI, TEPS, YMRS total scores.
  - H0: The 95% confidence interval for the effect of drug (TS-161 minus placebo) on [all listed outcomes] at the timepoints listed in the Schedule of Events after controlling for baseline scores, will include zero.
  - HA: The 95% confidence interval for the effect of drug (TS-161 minus placebo) on [all listed outcomes] at the timepoints listed in the Schedule of Events after controlling for baseline scores, will be less than and exclude zero.

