## 9.4.3 Analysis of the Secondary Endpoints

Secondary objectives are to evaluate the remission and response rates on the primary outcome measure (MADRS). A similar model to the one described above will be employed, with the difference that the outcome distribution will be specified as binary logistic. Because remission/response is determined based on change from baseline within a period, no baseline covariate will be included in the model. The parameter estimate for the effect of drug on remission/response rate at a given time point will be expressed as an odds ratio with a 95% CI. The remaining secondary analyses of clinical outcomes measured on the interval level (HAMD, BPRS, CADSS, C-SSRS, HAM-A, PANAS, SHAPS, SSI, TEPS, and YMRS) will be conducted in the manner described above for MADRS score. Following the current guidelines of the American Statistical Association (Wasserstein, Schirm et al. 2019), no threshold will be applied to secondary outcomes of this trial. Instead, parameter estimates will be presented alongside both their 95% confidence intervals and the raw p-value.

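### Section 8.4.1 promises a four-item BPRS positive-symptom index, but the endpoints and analysis use only the BPRS total

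*Combined protocol and SAP*

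**What the plan says.** The BPRS entry in Section 8.4.1 sets up two scores. For the first it states: "Four key BPRS items will be used as an index of positive symptoms of schizophrenia". The items are unusual thought content, suspiciousness, hallucinatory behavior and conceptual disorganization. For the second: "Three key BPRS items, blunted affect, emotional withdrawal, and motor retardation are selected as a measure of negative symptoms of schizophrenia".

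The endpoint and analysis sections use neither score. The endpoint for objective 6 in Section 3 is "Incidence of AEs and total scores using the Clinician Administered Dissociative States Scale (CADSS), Young Mania Rating Scale (YMRS), the Brief Psychiatric Rating Scale (BPRS", followed by other safety measures. The synopsis (Section 1.1) also specifies totals. Section 9.1.2 lists "Change from baseline in HDRS, BPRS, CADSS, C-SSRS, HAM-A, MADRS, PANAS, SHAPS, SSI, TEPS, YMRS total scores". For every scale on that list, the stated alternative is that the confidence interval for TS-161 minus placebo lies below zero, which for the BPRS is improvement. Section 9.4.3 groups the scale with others, "The remaining secondary analyses of clinical outcomes measured on the interval level (HAMD, BPRS, CADSS, C-SSRS, HAM-A, PANAS, SHAPS, SSI, TEPS, and YMRS", and applies the MADRS mixed model.

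Section 2.1 says why this scale matters: the trial hopes to show that an mGlu2/3 antagonist "produces antidepressant effects without psychotomimetic side effects".

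In the rating schedule (Section 1.4), the BPRS is taken on Day -1, at +230 min on Day 0, on Day 1 and on Day 21. Condition 2 repeats this on Days 34, 35, 36 and 56. In Section 1.3 the last dose of Condition 1 is on Day 20, where the row includes "Neurocognitive Battery Imaging: fMRI/MRS, MEG Study Drug Administration: TS-161/ Placebo (100mg or 50mg"; the period "Day 21 to Day 34" is washout.

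**The concern.** The methods section commits to a score that the analysis plan then leaves out, and that score is the one closest to the question. The four items are the direct BPRS measure of psychotomimetic change. The total adds them to items that need not move with them. Some of those, such as emotional withdrawal and motor retardation, could plausibly improve if the drug relieves depression. A flat total could then be reported as comparable to placebo although positive symptoms had risen.

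Two features add to this. The alternative in Section 9.1.2 points only towards improvement, so no stated BPRS hypothesis addresses worsening. And the safety hypothesis under objective 6 speaks of the timepoints measured over three weeks of treatment, whereas the BPRS is taken at the start of each condition and then not until dosing has ended.

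**Working it through.** The plan states no power or precision for the BPRS, so there is no BPRS figure to reproduce. The nearest benchmark is the MADRS calculation in Section 9.2: 20 patients, paired design, d = 0.70, two-sided 5%, stated power 80%. A noncentral-t calculation gives 84% at n = 20, and 19 patients suffice for 80%. That benchmark is borrowed below for scale only.

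**1. The score in each section.**

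| Section | BPRS score |
|---|---|
| 1.1 synopsis | total |
| 3, objective 6 | total |
| 8.4.1 | 4-item positive index; 3-item negative measure |
| 9.1.2 | total |
| 9.4.3 | BPRS, no index named |

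**2. Offset (invented item changes, named items only).** Let unusual thought content rise by 3 and each of the three negative items fall by 1.
- Change in total: +3 - (1 + 1 + 1) = 0
- Change in 4-item index: +3
- Change in 3-item measure: -3

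This shows that the total can hide such a pattern, not that it is likely to.

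**3. Dilution without any offset.** Assume only the four items move, all item change scores have the same SD, and every pair of items has correlation r. The SD of a sum of m items is proportional to √(m + m(m - 1)r). The effect size on a k-item total is therefore that of the index multiplied by √[(4 + 12r) / (k + k(k - 1)r)].

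With k = 7 and r = 0: √(4/7) = 0.756, and 0.70 × 0.756 = 0.53. With k = 7 and r = 0.3: √(7.6/19.6) = 0.623, and 0.70 × 0.623 = 0.44.

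The documents do not give the number of BPRS items; they name seven. The range of k is therefore an assumption, as are r and an index effect of d = 0.70.

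| k | d, r = 0 | power, n = 20 | d, r = 0.3 | power, n = 20 |
|---|---|---|---|---|
| 4 (index) | 0.70 | 84% | 0.70 | 84% |
| 7 | 0.53 | 61% | 0.44 | 46% |
| 12 | 0.40 | 40% | 0.27 | 21% |
| 18 | 0.33 | 29% | 0.18 | 12% |
| 24 | 0.29 | 23% | 0.14 | 9% |

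**4. Ratings against dosing days.** Each condition has 21 dosing days (Days 0 to 20; 35 to 55).
- BPRS: 2 of 21 (Days 0 and 1; 35 and 36), leaving 21 - 2 = 19 dosing days with none. The later rating, on Day 21 or 56, is about a day after the last dose.
- CADSS: 6 of 21 (Days 0, 1, 2, 3, 7 and 14; 35, 36, 37, 38, 42 and 49).

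**The case against.** Several replies are fair.

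- **The two texts can coexist.** Section 8.4.1 does not say the index replaces the total, and the items are collected anyway, so both could be reported. This stands, and it is why the fix adds the index and keeps the total. It does not excuse leaving a promised score out of Section 9.
- **The consequences are limited.** This is a secondary safety scale. Section 9.4.3 applies no significance threshold to secondary outcomes and reports intervals and p-values, so an interval above zero would be visible. That also stands. The power figures therefore measure lost sensitivity, not a changed decision rule.
- **The cancellation is hypothetical.** The documents give no BPRS baseline levels or item changes. That the three items would improve with mood is an inference. Dilution does not depend on it.

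A reader might go further and infer that the schedule lets a psychotomimetic effect go undetected. The documents do not support that. The +230 min rating follows a 100 mg first dose and covers an acute first-dose effect. The CADSS and AE assessments are both scheduled on Days 2, 3, 7 and 14. Section 7.1 asks, as far as possible, for final-day data at discontinuation, and the final day includes a BPRS. What remains is partial: the CADSS measures dissociation, not the four positive symptoms.

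The Phase 1 dissociation event might also be read as a warning for this trial. Section 2.2.10.5 places both TS-161 discontinuations at 150 mg, above this trial's maximum, and dissociation is what the CADSS measures.

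Nor can it be said that the drug is gone by Day 21. At the 1 to 5 h half-life in Section 2.2.10.3, at most 2^(-24/5) = 3.6% remains after 24 h, but that half-life is from rats and monkeys. At an assumed 12 h it would be 2^(-24/12) = 25%. Plasma decay also does not settle how long a central effect lasts.

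**Conclusion.** The point holds for the score. Section 8.4.1 commits to a four-item index and selects a three-item measure; Sections 1.1, 3, 9.1.2 and 9.4.3 use neither. Followed as written, the analysis tests the no-psychotomimetic-effect aim with a less sensitive score, and the only stated alternative is improvement. Under the assumptions above (index d = 0.70, equal item SDs, r from 0 to 0.3, other items unmoved), power falls from 84% to between 61% and 46% for a seven-item total, and further with more items. The documents show that masking is possible, not that it will happen.

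On timing, the supportable conclusion is narrow. BPRS evidence covers the first dose, Day 1 and the day after the last dose of each condition. It does not speak to the 19 dosing days between, which the CADSS and AE assessments cover in part. The primary MADRS conclusion is unaffected.

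**What to change.** In Section 3 (objective 6), Section 9.1.2 and Section 9.4.3:
- add the four-item positive-symptom index as a BPRS safety endpoint, with a two-sided hypothesis so that worsening is addressed;
- report the three-item measure separately;
- keep the total alongside.

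The synopsis should match. The items are already rated, so the cost is a few lines of text and two further outputs.

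State in the analysis plan that BPRS conclusions are limited to the occasions rated, and that the CADSS and AE assessments cover part of the interval between.

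Optionally, add the BPRS at existing CADSS visits such as Days 7 and 14 (42 and 49), at the cost of a slightly longer rating session. Moving the end-of-condition BPRS and CADSS to Day 20 or 55 is a weaker choice: it leaves Days 2 to 19 without a BPRS, gives up the Day 21 and 56 ratings, and crowds a day that already holds imaging and the neurocognitive battery.
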